2.8.3 Indocyanine green angiography (ICG)

The number and percentage of lesion type (only at Baseline) (type 1 / type 2 / type 3 / type 1 with aneuvrism / polyps) at Baseline will be provided.

The summary statistics (n, mean, std, median, min and max) for area of lesion associated with CNV (mm²) at Baseline and Week 12 will be provided along with summary statistics for change from Baseline and percentage change from Baseline at week 12 for area of lesion.

The above analysis will be done on both eyes. The analysis will be performed on the FAS.

2.8.4 Intraocular pressure

Intraocular pressure will be collected in the CRF at Baseline and Week 48. The summary statistics of IOP for nAMD patients will be presented at Week 48 along with change from Baseline and percentage change from Baseline in IOP. In addition, the number and percentage of patients with IOP ($\leq 10, 10\text{-}25, 25\text{-}30 \text{ and } \geq 30 \text{ [mmHg]}$) will be presented at Week 48.

The above analysis will be done on both eyes. The analysis will be performed on the FAS.

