- Any significant increase in CRT (based on investigator assessment).
- Retinal hemorrhage.
- Intraretinal fluid or SRF due to disease activity (degenerative cysts allowed).
- Increase of sub-RPE fluid.

These criteria are for guidance only, the investigator may define disease activity based on his/her own assessment.

A patient who misses Week 16 will undergo the disease activity assessment at Week 20 as he/she would have done if the visit had not been missed. If, however, a patient misses any of the following disease activity assessment visits (Week 20, Week 32) then the patient will be assumed to have met the disease activity criterion at the missed visit and will be reassigned to a q8w regimen up to study exit.

If a patient misses Week 12, then the Week 8 values will be applied as the reference for disease activity assessments up to and including Week 44.

Fluorescein angiography: Fluorescein angiography (FA) is a diagnostic procedure that uses a special camera to record the blood flow in the RETINA – the light sensitive tissue at the back of the eye.

Color fundus photography (CFP): CFP is a diagnostic procedure that involves the use of a device known as a fundus camera to record colored images of the interior surface of the eye. The goal of this procedure is to monitor the presence of disorders and their change with time.

Fundus autofluorescence (FAF): Fundus autofluorescence imaging is an *in vivo* imaging method for metabolic mapping of naturally or pathologically occurring fluorophores of the ocular fundus.

Indocyanine green angiography (ICG): ICG is a diagnostic procedure that uses ICG dye to examine the blood flow in the choroid – the layer of blood vessels that lies underneath the retina. ICG is injected into a vein in the arm/hand. As the dye passes through the blood vessels of the eye, photographs are taken to record the blood flow.

Intraocular pressure (IOP): IOP is the fluid pressure of the eye. IOP is measured in millimeters of mercury (mmHg). Normal eye pressure is usually considered to be between 10 and 25 millimeters of mercury (mmHg).

Fundus examination: Fundus examination used to assess diagnose vitro-retinal diseases (such as retinal haemorrhage, vitreal haemorrhage, retinal tear and detachment), optic nerve defects and hereditary diseases.

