 - Volume (mm³) and height (μm) of each fluid (in case of presence)
 - 1. Intraretinal fluid

- 2. Subretinal fluid
- 3. Sub-RPE fluid
- In case of sub-RPE / PED : nature : serious PED / fibrovascular PED / mixed PED
- OCT-A (analyzed by Vienna)
 - 1. CNV location (only at Baseline)
 - 2. CNV lesion area (at the biggest surface) (mm²/µm²)
- Fundus observation
 - 1. Retinal hemorrhage (none, retinal macular and retinal non-macular)
 - 2. Presence of vitreal hemorrhage (Yes, No)
 - 3. Retinal tear/ detachment (none, tear, detachment, both)
- Color fundus photography (CFP)
 - 1. Presence of retinal or subretinal hemorrhage (Yes, No)
 - 2. Presence of fibrosis (Yes, No)
 - 3. Presence of atrophy (Yes, No)
 - 4. Subretinal blood affecting foveal center point and/ or > 50% of total lesion (Yes, No)
- Fundus autofluorescence (FAF)
 - 1. Presence of macular atrophy (Yes, No)
 - 2. Area of macular atrophy
- Intraocular pressure
- Intraocular pressure (≤ 10 , 10-25, 25-30 and ≥ 30 [mmHg])
- Disease activity assessment (Present)
- History of primary diagnosis:
 - 1. Disease (neovascular age-related, macular degeneration [nAMD])
 - 2. Age of diagnosis
 - 3. Eye (OD, OS)
 - 4. Ongoing (Yes, No)
- History or evidence of the following in the study eye within the 90-day period prior to Screening/Baseline:
 - 1. Intraocular or refractive surgery
 - 2. Previous panretinal photocoagulation
 - 3. Previous submacular surgery, other surgical intervention or laser treatment for nAMD including photodynamic therapy (PDT)
- Concomitant medication at Baseline
- Medical history
- Co morbidities

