2.9 Safety analyses

Safety measurements include duration of exposure, vital signs and adverse events. All safety endpoints will be summarized using the Safety Set. Patients will be analyzed according to treatment received. No imputation will be carried out for missing data.

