2.9.4 Other safety data

Not applicable

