5.5 Rule of exclusion criteria of analysis sets

Table 5-1 Protocol deviations that cause patients to be excluded

Deviation ID	Description of Deviation	Exclusion in Analyses	Severity code
INCL01	Signed informed consent not obtained	Excluded from FAS and PPS analysis	1
INCL02	Age less than 50 year	Included in everything	0
INCL03	No active CNV lesions	Excluded from FAS and PPS	1
INCL04	No Intra- and/or subretinal fluid	Excluded from FAS and PPS	1
INCL05	Study eye BCVA out of range	Excluded from PPS	2
EXCL01	Active infection in either eye	Excluded from PPS	2
EXCL02	Fellow eye ocular disease	Included in everything	0
EXCL03	Poor quality images	Included in everything	0
EXCL03a	History of IOI	Included in everything	0
EXCL05	Study eye lesion area ≥50%	Included in everything	0

Deviation ID	Description of Deviation	Exclusion in Analyses	Severity code
EXCL05a	Study eye atropathy or fibrosis	Included in everything	0
EXCL07	Study eye concomitant condition	Included in everything	0
EXCL08	Study eye macula damage	Included in everything	0
EXCL09	Study eye vitreous hemorrhage	Included in everything	0
EXCL10	Study eye uncontrolled glaucoma	Included in everything	0
EXCL11	Study eye aphakaia	Included in everything	0
EXCL12	Other treatment in study eye	Excluded from PPS	2
EXCL13	Steroids in study eye	Included in everything	0
EXCL14	Prior keratoplasty/vitrectomy	Included in everything	0
EXCL15	Study eye previous ocular treatment	Included in everything	0
EXCL16	End stage renal disease requiring dialysis or renal transplant	Included in everything	0
EXCL17	Systematic drug toxic to eye	Included in everything	0
EXCL18	Participation in another study	Excluded from PPS	2
EXCL19	Systematic anti-VEGF therapy	Included in everything	0
EXCL20a	Stroke or myocardial infraction	Included in everything	0
EXCL21	Uncontrolled blood pressure	Included in everything	0
EXCL22	Malignancy	Included in everything	0
EXCL22a	Medical condition impact	Included in everything	0
EXCL24	Hypersensitivity	Included in everything	0
EXCL25	Pregnant or nursing woman	Included in everything	0
EXCL26	Women of childbearing potential	Included in everything	0
EXCL27	Minor or protected adult	Excluded from PPS	2
COMD01	Prohibited medication/procedures	Included in everything	0
COMD02	Steroids use 5 days prior to IP	Included in everything	0
TRT01	Wrong IP administered	Excluded from PPS	2
TRT02	Incorrect dose administered	Excluded from PPS	2
TRT03	Pregnancy but not discontinued	Included in everything	0

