TRT04	Short treatment window between treatment	Included in everything	0
TRT05	Treatment > 3 days after injection visit	Included in everything	0
TRT06	Injection given at Week 12	Excluded from PPS	2
TRT07	Q8W IVT out of window	Included in everything	0
TRT08	Q12W IVT out of window	Included in everything	0
TRT09	COVID-19 Drug supply change	Included in everything	0

Deviation ID	Description of Deviation	Exclusion in Analyses	Severity code
TRT10	COVID-19 Treatment not given	Included in everything	0
TRT11	Missed Injection loading phase	Excluded from PPS	1
TRT12	Missed Injection	Included in everything	0
TRT13	No Disease activity but injection is given	Included in everything	0
TRT14	Treatment admin prior effic/safty evaluation	Included in everything	0
TRT15	Treatment given at EOS	Included in everything	0
WITH01	Withdrew consent not discontinued	Excluded from FAS and PPS	1
OTHER01	Patient rescreened > once	Included in everything	0
OTHER02	Severe ICH-GCP non-compliance	Excluded from FAS and PPS	1
OTHER03	New ICF is missing-rescreened	Excluded from FAS and PPS	1
OTHER04	Mishandling IP	Included in everything	0
OTHER05	Temperature excursion IP administered	Included in everything	0
OTHER06	Treatment regimen wrongly adjusted	Included in everything	0
OTHER07	Missed mandatory visit	Excluded from PPS	2
OTHER08	Missed injection visit	Included in everything	0
OTHER09	FA out of window	Included in everything	0
OTHER10	Rescreen due to BCVA results	Included in everything	0
OTHER11	Rescreen >14days w/o screening procedure	Included in everything	0
			1
OTHER13	COVID-19 Missed visit	Included in everything	0
OTHER14	COVID-19 Visit not at site	Included in everything	0
OTHER15	COVID-19 Assessment changed	Included in everything	0
OTHER16	COVID-19 Discontinuation Included in everything		0
OTHER17	Efficacy assessment not done Excluded from PPS		2
OTHER18	Safety assessment not done Included in everything		0
OTHER19	BCVA not done correctly Included in everything		0
OTHER20	Visit window > 7 days Included in everything		0
OTHER21	Vital signs/safety call not done Included in everything		0
OTHER22	Imaging analyzed after WoC Included in everything		0

Table 5-2 Patient Classification

Analysis Set	Severity codes that cause a subject to be excluded
ENR	NA
FAS	1
FAS-EST	1
PPS	1,2 (All specified PD in Table 5.1 due to COVID)
PPS-EST	1, 2 (All specified PD in Table 5.1 due to COVID-19)
SAF	NA

6 Reference

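### SAP 2.8.4 analyses intraocular pressure, a protocol safety assessment, as efficacy on the FAS at Week 48 only, in bands that cannot place 25 mmHg, with no rule for early-discontinuation readings

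*SAP*

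**What the plan says.** **Protocol.** Section 8.4 counts ophthalmic examinations among the safety assessments, and IOP is the first item of that examination in 8.4.3. Section 4.5 names transient and sustained IOP rises as a known risk. Section 12.5.2 assigns all safety analyses to the Safety Set. For ophthalmic examinations it plans a listing by patient and visit, plus summaries of clinically relevant abnormalities by visit or time. Table 8-1 (footnote 7) and 8.4.3 call for action at IOP >=25 mmHg.

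**SAP Addendum 1.0.** Section 2.8.4 sits within section 2.8, on other efficacy variables. It plans: "The summary statistics of IOP for nAMD patients will be presented at Week 48 along with change from Baseline". On eyes and analysis set it says: "The above analysis will be done on both eyes. The analysis will be performed on the FAS". The bands, which are the same in 2.3.4 for baseline, start at <=10 and continue "10-25, 25-30 and ≥ 30 [mmHg". Section 2.1.1 adds: "Normal eye pressure is usually considered to be between 10 and 25 millimeters of mercury (mmHg". Section 2.9 defines the safety scope as follows: "Safety measurements include duration of exposure, vital signs and adverse events". The entry under "2.9.4 Other safety data" is marked not applicable. Section 2.8.5 plans a by-patient listing for the fundus examination; 2.8.4 plans none for IOP.

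**The concern.** The SAP departs from the protocol on three points for a named risk of the drug: the section IOP is reported under, the analysis set, and the visits summarised.

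The only numeric post-baseline IOP table would describe patients with a Week 48 reading, taken 4 or 8 weeks after their last possible injection. Patients who stopped early include those who had to stop for intraocular inflammation or a safety risk (protocol 9.1.1). Their scheduled IOP reading is at the ETD visit, and the SAP assigns that reading to no summary. A value at the protocol's own action level cannot be classified from the bands as printed.

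**Working it through.** **1. Analysis set.** By definition (SAP 2.2) the FAS and the Safety Set are nearly the same. They separate in Table 5-2, under the column "Severity codes that cause a subject to be excluded": code 1 removes a patient from the FAS, and no code removes anyone from the Safety Set. Table 5-1 gives code 1 to, among others, INCL03 ("No active CNV lesions") and INCL04 (no intra- or subretinal fluid). TRT11 (missed loading injection) also has code 1, although its row says PPS only. An injected patient with such a deviation is in the Safety Set but not in the IOP table.

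**2. Bands.** With range ends read as inclusive:

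| Reading (mmHg) | Bands it fits |
|---|---|
| 10 | <=10 and 10-25 |
| 25 | 10-25 and 25-30 |
| 30 | 25-30 and >=30 |

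Every other whole-number value fits exactly one band. The inequality signs suggest an answer for 10 and 30. Nothing on either side settles 25. SAP 2.1.1 would count it as normal; the protocol acts on it.

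**3. Timing of ETD readings.** Inputs: Table 8-1 marks IOP at Day 1 and in the shared EOS/ETD column. ETD is 4 weeks after the last injection (footnote 11). Patients who have had ETD assessments need not repeat them at Week 48 (footnote 10; 9.1.1). In SAP Table 2-1 the scheduled post-baseline day is 7 x week, and the Week 48 window is Day 323-349.

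Injection weeks under the protocol regimen:
- q12w throughout: 0, 4, 8, 20, 32, 44
- q8w from Week 16: 0, 4, 8, 16, 24, 32, 40
- q8w from Week 20: 0, 4, 8, 20, 28, 36, 44
- q8w from Week 32: 0, 4, 8, 20, 32, 40

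An early stopper misses at least the final injection. The latest possible last injection is therefore Week 32, 32, 36 or 32 respectively, so Week 36 overall.
- Earliest nominal ETD: Day 1 + 28 = Day 29.
- Latest nominal ETD: 36 x 7 + 28 = 252 + 28 = Day 280, which is 323 - 280 = 43 days before the window opens.
- With visit +7, treatment +3 and ETD +7 days: 252 + 7 + 3 + 28 + 7 = Day 297, which is 26 days before. The +7 on ETD is an assumption; Section 3 gives it for the early-withdrawal visit.

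These figures apply when the stop is known by the 4-week point. No visits are planned between injection visits (6.7.2), so a patient injected at Week 32 (q12w) or Week 36 (q8w) next attends at Week 44, 44 x 7 = Day 308. If the stop is decided there, the 4-week point (Day 252 or 280) has passed and ETD falls on Day 308 or later. Day 308 itself lies in the Week 44 window (Day 295-321), where no IOP summary is planned. An ETD visit at least 323 - 308 = 15 days later would lie in the Week 48 window. Day 280 and Day 297 are therefore typical limits, not strict ones.

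**4. Which rule the SAP applies.** Section 2.1.2 says windows are used for data analysis. Section 2.1.1 says they apply to OCT and injection visits and does not name IOP. If IOP is windowed, most ETD readings enter no table. If it is tabulated by the EOS/ETD column, readings from about Day 29 onward would appear as Week 48. The SAP does not choose.

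**5. Scale.** The documents give no 48-week discontinuation rate. If 5%, 10% or 20% of 210 stop early (assumed), that is 210 x 0.05 = 10.5, 210 x 0.10 = 21, or 210 x 0.20 = 42 patients. They give no IOP distribution either. If readings are whole numbers, roughly normal with mean 14-16 and SD 3-4 mmHg (assumed), 0.02% to 0.80% would read exactly 25. Among 189 patients that is at most 189 x 0.0080 = 1.5.

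**The case against.** The strongest reply is that the safety content is already covered. A non-transient rise is to be treated (8.4.3), and a finding that needs therapy or is clinically significant is an adverse event (10.1.1), tabulated on the Safety Set (SAP 2.9). This largely stands and sets the severity. One small gap remains: SAP adverse-event tables stop 28 days after the last injection, so a rise first found at an ETD visit held later than that would be missing from them.

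Second, early stoppers may not be lost. Section 8 asks patients who discontinue treatment to return for the EOS assessments, and 9.1.1 repeats this where possible. This stands in part. Footnote 10 and a later sentence in 9.1.1 waive the repeat after ETD, so a return is possible but not required. A reader might infer that no early stopper's reading can ever reach the Week 48 table. The documents do not support that, given a voluntary return, a stop decided late, and the unclear scope of the windows.

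Third, few readings will be exactly 25, table shells can fix the edges, and exclusion criterion 10 uses >25 mmHg, which agrees with the SAP's normal range. All true, but the action rule during treatment is >=25, and the SAP text should settle the edge.

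Fourth, a reader might infer that the Week 48 table understates the rate of raised IOP. Nothing in the documents shows that rates differ between completers and early stoppers. If they are equal there is no shift.

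**Conclusion.** The point holds, as a minor one. SAP 2.8.4 departs from protocol 12.5.2 on section, analysis set, listing and visits. Its bands overlap at 10, 25 and 30 mmHg, so the action level cannot be placed. Most ETD readings, nominally Day 29 to Day 280, precede the Week 48 window, and the SAP does not say whether IOP is windowed or whether ETD readings are pooled with Week 48.

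The analysis-set and band findings rest on the text alone. The timing finding also assumes that the stop is known by the 4-week point. The number of patients affected and any change in an IOP rate cannot be derived from the documents; the counts above are assumptions that show scale only. IOP is not an endpoint, and the primary analysis and sample size are untouched.

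**What to change.** In the SAP:
- Move IOP to section 2.9 and analyse it on the Safety Set.
- In 2.3.4 and in the moved section, use <=10, >10 to <25, 25 to <30 and >=30 mmHg, and report n (%) with >=25. Align the normal range in 2.1.1.
- List all captured IOP values by patient and visit.
- Summarise ETD and early-withdrawal readings in their own row, with change from baseline, and state that they are not pooled with Week 48. They come from different times and exposures.

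First confirm that ETD IOP reaches the eCRF. Section 8.4.3 limits capture to Screening/Baseline, Week 48/EOS and adverse events, while another sentence there has pre-dose values entered for either eye. If ETD readings are not captured, the row cannot be filled, and the SAP should say so.

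Cost: SAP wording, new band edges, one listing and one table row. No protocol or site change is needed, and routine eCRF capture of injection-visit IOP is not requested.

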2.8.5 Fundus examination

The below variables of number and percentage will presented for study eye and fellow eye by visit.

- Retinal hemorrhage (none, retinal macular and retinal non-macular)
- Presence of vitreal hemorrhage (no, yes)
- Retinal tear/detachment (0- none, 1- retinal tear, 2- retinal detachment, 3- retinal tear and detachment)
- Presence of intraocular inflammation (no, yes)
- Presence of vasculitis.

Listing of fundus examination parameter will be provided by patient and visit.

The above analysis will be done on the both eye. The analysis will be performed on the FAS.

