## Unscheduled visits

If a patient returns to the site prior to his/her next scheduled study visit, the investigator will capture the unscheduled visit in the eCRF only in the case of a clinically significant abnormal finding.

If this finding leads to an AE and/or the decision to treat the patient prior to his/her next scheduled treatment, all the procedures listed for the Interim Visit need to be conducted and captured in the eCRF.

In the case of a treatment decision for nAMD treatment is made during the unscheduled visit (at the exception of AE treatment), the assigned study medication can not be administrated. In case of administration of an anti-VEGF medication during an unscheduled visit, it will be considered as the use of a prohibited treatment and should be managed as described in [Section 9.1.1](#).

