- **Posterior segment (indirect fundus) examination** will be conducted by the investigator at the Screening/Baseline Visit for both eyes. An examination of the peripheral retina must also be conducted to ensure that the IVT injection can safely be performed. Posterior segment examination must be performed carefully before each study treatment. The results of the examination including any abnormalities (e.g. vitreous cells/haze, retinal tear/detachment, hemorrhage and vascular occlusion, vasculitis, etc.) should be recorded in the source documents. If there are any signs of IOI, vitreous cells and haze should be assessed using National Institutes of Health (NIH) grading system (Nussenblatt et al 1985). The outcome of the examination will be documented in the source document (e.g. ophthalmic examination tool) and appropriate eCRF page as applicable.
- The fundus examination and FAF will be performed at the ophthalmic exam visits indicated in the visit assessment schedule (Table 8-1) for the study eye only. Except for Screening/Baseline visit and Week 48/EOS Visit, the fellow eye will be examined at the discretion of the investigator. The results of the examination of either eye must be recorded in the source documents.

Pupil dilation for slit lamp examination and indirect ophthalmoscopy is optional according to investigator practice.

Clinically significant abnormal findings (as judged by the investigator) from the slit lamp or ophthalmoscopy observations should be recorded as an AE in the eCRF.

A phone call one week after the first injection (a window for the phone call is +7 days) must be made to check whether there are any changes in vision or any symptoms of intraocular inflammation. It should be documented in the source document. From the second injection onwards, similar phone calls should be made at investigator's discretion per local practice.

**Instruct the patient to contact the site for any changes in vision or any symptoms of inflammation between scheduled visits.** Every effort should be made to bring the subject for immediate examination.

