### **12.5.2 Safety endpoints**

For all safety analyses, the Safety Set will be used.

The secondary safety endpoint of this study is as follows:

- Incidence of AEs (serious and non serious) reported in patients treated with brolocizumab.

Safety summaries (tables, figures) include only data from the on-treatment period with the exception of Baseline data, which will also be summarized where appropriate (e.g. change from Baseline summaries). In addition, a separate summary for death including on treatment and post treatment deaths will be provided. In particular, summary tables for adverse events of special interest (AESIs) will summarize only on-treatment events, with a start date during the on-treatment period (treatment-emergent AEs).

The on-treatment period lasts from the date of first administration of IVT injection of study treatment to 30 days after the date of the last actual administration of IVT injection of study treatment.

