### Other safety evaluations

All ophthalmic examinations data will be listed by patient and visit and if normal ranges are available, abnormalities will be flagged. In addition, summary statistics for clinically relevant abnormalities will be provided by visit/time.

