2.1.2 Visit windows for data analysis

Visit windows will be used for the data analysis, as per the planned visits in the protocol. During the q12w/q8w phase, i.e., from Week 16 to Week 44, the treatment visit intervals will be determined by the investigator, based on the patient's disease activity.

Table 2-1 Assessment windows for scheduled visits

Analysis Visit	Week	Scheduled Day	Visit Window
Screening/Baseline	BL	1	-14 days to Day 1*
Week 4	4	28	Day 22 - 34
Week 8	8	56	Day 50 – 62
Week 12	12	84	Day 71 – 97
Week 16	16	112	Day 99 – 119
Week 20	20	140	Day 127 – 153
Week 24	24	168	Day 155 – 182
Week 28	28	196	Day 183 – 209
Week 32	32	224	Day 211 – 237
Week 36	36	252	Day 239 – 265
Week 40	40	280	Day 267 – 293
Week 44	44	308	Day 295 – 321
Week 48	48	336	Day 323 - 349

* Baseline measurement before the first treatment administration.

If study visit assessments and the corresponding treatment occur on separate days, a repeat safety check-up should be performed prior to treatment of the eye and results documented in the source documents. If any safety concern arises related to the study eye that, in the opinion of the investigator, may be further impacted by the study treatment or injection procedure, treatment needs to be cancelled. Injections are contraindicated in patients with active intraocular or periocular infections and in patients with active intraocular inflammation; therefore, the investigators should verify that these conditions are not present in the study eye prior to every injection. Any AEs must be recorded in the eCRF.

The injection procedure for brolucizumab will be performed according to local clinical practice. Injections will be administered by the investigator.

Data collected at unscheduled visits will not be used in 'by-visit' tabulations or graphs and will be presented in listings.

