2.8 Analysis of other efficacy variables

2.8.1 Color fundus photography

The number and percentage will be provided at Screening/Baseline, week 12 and end of study (Week 48) for below questions:

- Was color fundus photography performed? If not, then reason for not performed CFP.
- Presence of retinal hemorrhage in central subfield.
- Presence of subretinal hemorrhage in central subfield.
- Presence of fibrosis in the central subfield the diameter of 3000 μm.
- Presence of atrophy in the central subfield the diameter of 3000 μm.
- Is there subretinal blood affecting the foveal center point and/or >50% of total lesion.
- Presence of Vasculitis.

The above analysis will be done on both eyes. The analysis will be performed on the FAS.

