2.9.4.2 Vital signs

Vital signs will include blood pressure and pulse rate measurements.

All vital signs data will be listed by patient, and visit, and if ranges are available, abnormalities will be flagged. Abnormal values are marked in Section 5.3. All data, including data from unscheduled visits, will be considered when identifying abnormal values. Analysis of vital sign measurements using summary statistics for the change from Baseline for each post-Baseline

visit will be performed. These descriptive summaries will be presented for each vital sign. Change from Baseline will only be summarized for patients with both Baseline and post-Baseline values.

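### Fundus findings of IOI and vasculitis are summarised as efficacy, on the FAS and at scheduled visits only, and some late-onset cases can miss every summary table of these events

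*SAP*

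**What the plan says.** The protocol treats ophthalmic examination as safety. Section 8.4 lists it among the safety assessments. Section 12.5.2 states "For all safety analyses, the Safety Set will be used", and its paragraph on other safety evaluations covers ophthalmic examinations and promises that "summary statistics for clinically relevant abnormalities will be provided by visit/time".

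The SAP places it elsewhere. The fundus examination (2.8.5) sits under the heading "2.8 Analysis of other efficacy variables". Five findings (retinal haemorrhage, vitreal haemorrhage, tear/detachment, IOI, vasculitis) are counted by visit and eye, with the instruction "The above analysis will be done on the both eye. The analysis will be performed on the FAS". SAP 2.9 names only exposure, vital signs and adverse events as safety measurements, and 2.9.4 (other safety data) is marked as not applicable.

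On unscheduled visits, SAP 2.1.2 says: "Data collected at unscheduled visits will not be used in 'by-visit' tabulations or graphs and will be presented in listings". For vital signs, SAP 2.9.4.2 takes a different line: "All data, including data from unscheduled visits, will be considered when identifying abnormal values".

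The protocol expects eye problems to surface between visits. Patients with symptoms are to contact the site, and "Every effort should be made to bring the subject for immediate examination" (8.4.3). An unscheduled visit is recorded in the eCRF only when it shows a clinically significant abnormality. If that leads to an adverse event, "all the procedures listed for the Interim Visit need to be conducted and captured in the eCRF" (section 8, Unscheduled visits).

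**The concern.** IOI, retinal vasculitis and retinal vascular occlusion are this study's adverse events of special interest (AESIs), and Amendments 2 to 4 all changed the protocol because of them. The fundus examination is the direct clinical record of two of the three. Filed under efficacy, it is analysed on a set that can be smaller than the Safety Set. It is also summarised only at scheduled visits, although the unscheduled examinations that reach the eCRF are by design those with a significant abnormality.

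Two things are at stake. The examination table may be unable to corroborate the AESI counts. And a case that also falls outside the window of the AE tables would be visible only in listings, and possibly in the AESI timing plots.

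**Working it through.** **1. Analysis sets.** SAP 2.2 defines the FAS as patients assigned study treatment who received at least one injection, and the Safety Set as patients with at least one injection. In a single-arm study these are the same people. Table 5-2, however, excludes severity code 1 from the FAS and applies no exclusion to the Safety Set. In Table 5-1, INCL03 (no active CNV) and INCL04 (no intra- or subretinal fluid) carry code 1 and are marked as excluded from FAS and PPS. A treated patient with either deviation is in the Safety Set but not in the FAS, so the tables contradict the FAS definition. TRT11 (missed loading injection) adds a second contradiction: its row excludes from the PPS only, but its code is 1, which Table 5-2 makes a FAS exclusion.

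**2. Which summary would show an IOI case.** There are two candidates.
- The fundus table in SAP 2.8.5: scheduled visits only, FAS.
- The AE and AESI tables in SAP 2.9.1 and 2.9.1.1: Safety Set and any type of visit, but only events starting in the on-treatment period. SAP 2.1.1 ends that period 28 days after the last actual injection. Protocol 12.5.2 uses 30 days and applies the limit to the AESI tables by name.

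**3. The gap between them.** Protocol 9.1.1 requires study treatment to stop when IOI develops, so the injection before the event becomes the last one. The part of a dosing interval beyond the on-treatment window is:
- q12w, 28-day rule: 84 − 28 = 56 days; 56/84 = 67%
- q12w, 30-day rule: 84 − 30 = 54 days; 54/84 = 64%
- q8w, 28-day rule: 56 − 28 = 28 days; 28/56 = 50%
- q8w, 30-day rule: 56 − 30 = 26 days; 26/56 = 46%

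These are shares of calendar time, not of events; the documents do not give the timing of IOI within an interval.

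**4. Worked case.** A q12w patient is injected at Week 20 and develops IOI 42 days later. No visit is planned between Weeks 20 and 32, so it is seen at an unscheduled visit. Day 42 is beyond both 28 and 30, so the event is outside the AE and AESI summary tables. The visit is unscheduled, so it is outside the fundus table. Later examinations may not recover it. In Table 8-1 the column for patients continuing after early treatment discontinuation (ETD) has medications, adverse events and BCVA but no ophthalmic examination, and the Week 48 EOS assessments are not required of them. An ETD examination could still show the signs. But its nominal time, 4 weeks after the last injection, has already passed in this example, and SAP Table 2-1 has no ETD row.

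**5. Scale.** The plan's 210 patients reproduce: 1.96 × 35/√189 = 4.99, and 189/0.9 = 210. As an assumption only, apply the IOI-related AE rates in protocol 4.5 (3.2% in men, 5.3% in women, pivotal studies): 210 × 0.032 = 6.7 and 210 × 0.053 = 11.1, so about 7 to 11 patients. One omitted case would then be 1/11 = 9% to 1/7 = 14% of the cases. How many would fall in the gap cannot be derived from the documents.

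**The case against.** The strongest reply is that the IOI safety analysis is the AESI section, not 2.8.5. Protocol 8.4.3 requires clinically significant slit-lamp or ophthalmoscopy findings to be recorded as adverse events. SAP 2.9.1.1 summarises AESIs on the Safety Set by type, per patient and per 1000 injections, whatever the visit type. Fundus data and unscheduled data are listed. The protocol itself asks for summaries by visit or time, which 2.8.5 provides. The vital-signs rule covers the flagging of abnormal values and plans no any-time occurrence table. All of this stands, and it limits the point. It does not close the gap in the worked case, because the AE and AESI tables carry the on-treatment cut-off.

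Some stronger readings are tempting but unsupported:
- A reader might infer that a loading dose withheld for IOI would be coded TRT11, so that the IOI case itself leaves the FAS. Table 5-1 lists deviations, and withholding an injection when IOI signs are present follows protocol 6.7.2. No text says it would be coded that way. The other code-1 items have no stated link to IOI.
- Colour fundus photography is not misplaced: protocol 8.3 lists it as an efficacy assessment.
- Routine slit-lamp results go to source documents, and with IOI signs to the eCRF only as applicable, so a dataset to tabulate is not shown to exist.
- Retinal vascular occlusion has no fundus row, but it is in the AESI derivation (SAP 5.4). A row filled from AE records could not corroborate those same records.

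**Conclusion.** The point holds as a misplacement with a limited but real gap in the summaries. The SAP departs from the protocol by handling fundus findings as efficacy on the FAS. Tables 5-1 and 5-2 make that set smaller than the Safety Set whenever a treated patient has a code-1 deviation. Unscheduled examinations do not enter the table.

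A reader might infer that IOI cases drop out of the safety picture altogether. The documents do not support that: on-treatment AESIs are summarised on the Safety Set, and treatment-emergent adverse events and fundus findings are listed. The uncovered case is narrower: onset more than 28 days after the last injection (30 by the protocol), first seen at an unscheduled visit, and not still visible at a later examination that the by-visit table includes. Its frequency is unknown. The 7 to 11 expected IOI patients rest on assuming that the pivotal-study rates apply here, and serve only to show the weight of a single case. The change should be made because the information is already collected and the study's safety question is this one.

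**What to change.** 1. Report the 2.8.5 fundus findings under SAP 2.9.4, on the Safety Set, by eye.
2. Keep the by-visit rows. For each finding already collected (IOI, vasculitis, tear/detachment, retinal and vitreal haemorrhage), add one row for any post-baseline occurrence, using scheduled, unscheduled and ETD examinations.
3. Cross-check patients with IOI or vasculitis on examination against the AESI records, and explain any mismatch in the CSR.
4. Reconcile the TRT11 row and the FAS definition in SAP 2.2 with Table 5-2, and state one length for the on-treatment period in place of 28 days in the SAP and 30 in the protocol.

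The cost is SAP wording and table programming, with no new procedures or visits. Reported counts of IOI and vasculitis may rise slightly.
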